### **Neurology Evaluations**

Patients will undergo a NIHSS and EQ5D prior to procedure (within 24 hours) and post (12-48 hours). If changes in the NIHSS score of greater than 3 a neurologist will be consulted, and the patient will be evaluated and treated based on their recommendation. Asymptomatic Cerebrovascular emboli are defined as cerebral infarct present on MRI or CT scan for which no corresponding symptoms were documented [2]. Symptomatic Cerebrovascular emboli were defined as an episode of neurological dysfunction associated with a focal cerebral infarction in the region correlating with the dysfunction. .

### **Study Population**

For entry into the study, the following criteria MUST be met.

#### ***Inclusion Criteria***

##### **A. Signed Written Informed Consent**

Before any study procedures are performed, subjects will have the details of the study described to them, and they will be given a written informed consent document to read. Then, if subjects consent to participate in the study, they will indicate that consent by signing and dating the informed consent document in the presence of study personnel.

##### **B. Target Population**

- Patients undergoing radiofrequency catheter ablation for left ventricular arrhythmias secondary to ischemic cardiomyopathy and non-ischemic cardiomyopathy. Patients with normal heart VT, i.e. no clinical evidence of cardiomyopathic process will be excluded from the study.
- Patients undergoing radiofrequency catheter ablation for left sided VT based on initial clinical suspicion.

### **C. Age and Reproductive Status**

- Males and Females, ages 18 to 80 years
- Women of childbearing potential (WOCBP) must have a negative serum or urine pregnancy test (minimum sensitivity 25 IU/L or equivalent units of HCG) within 24 hours prior to the start of study drug.
- Women must not be breastfeeding
- WOCBP must agree to follow instructions for method(s) of contraception for the duration of treatment with DOAC plus 5 half-lives of DOAC (3 days) plus 30 days (duration of ovulatory cycle) for a total of 33 days post-treatment completion.
- Males who are sexually active with WOCBP must agree to follow instructions for method(s) of contraception for the duration of treatment with DOAC plus 5 half-lives 3 days) plus 90 days (duration of sperm turnover) for a total of 93 days post-treatment completion.
- Azoospermia males and WOCBP who are continuously not heterosexually active are exempt from contraceptive requirements. However, they must still undergo pregnancy testing as described in this section.

Investigators shall counsel WOCBP and male subjects who are sexually active with WOCBP on the importance of pregnancy prevention and the implications of an unexpected pregnancy. Investigators shall advise WOCBP and male subjects who are sexually active with WOCBP on the use of highly effective methods of contraception. Highly effective methods of contraception have a failure rate of < 1% when used consistently and correctly.

At a minimum, subjects must agree to the use of one method of highly effective contraception as listed below:

## **HIGHLY EFFECTIVE METHODS OF CONTRACEPTION**

- Male condoms with spermicide
- Hormonal methods of contraception including combined oral contraceptive pills, vaginal ring, injectable, implants and intrauterine devices (IUDs) such as Mirena by WOCBP subject or male subject's WOCBP partner. Female partners of male subjects participating in the study may use hormone based contraceptives as one of the acceptable methods of contraception since they will not be receiving study drug
- IUDs, such as ParaGard
- Tubal ligation
- Vasectomy.
- Complete Abstinence\*

\*Complete abstinence is defined as complete avoidance of heterosexual intercourse and is an acceptable form of contraception for all study drugs. Female subjects must continue to have pregnancy tests. Acceptable alternate methods of highly effective contraception must be discussed in the event that the subject chooses to forego complete abstinence.

### ***Exclusion Criteria***

#### **A. Target Disease Exceptions**

- History of CVA/TIA in last 3 months
- Cardiac surgery or neurosurgery within 3 months of the intended procedure date

## **B. Medical History and Concurrent Diseases**

- Ongoing ischemia or a prior coronary intervention requiring continued dual antiplatelet therapy
- Any active bleeding
- Severe hypersensitivity reaction to DOACs (including drug hypersensitivity, such as skin rash and anaphylactic reactions, such as allergic edema)
- Prosthetic heart valves; the safety and efficacy of DOACs have not been studied in patients with prosthetic heart valves.
- History or bleeding and clotting disorders
- Requires dual anti-platelet therapy
- Contraindications to Aspirin therapy
- Contraindication to oral anticoagulation
- Patients who have a continuing need for oral anticoagulation (i.e. patients with AF; DVT or a mechanical valve) Evidence of intracardiac thrombus
- Patient with Creatinine Clearance of  $\leq 40$  cc/min

## **C. Sex and Reproductive Status**

*See Section on WOCBP above*

## **D. Prohibited Treatments and/or Therapies**

- Participation in another investigational study related to oral anticoagulation, drug and/or device intervention.
- Claustrophobic patients
- ICD generator placement before the year 2000
- Has an ICD and is pacing dependent without underlying rhythm upon interrogation at baseline
- Patient has abandoned leads

### **E. Other Exclusion Criteria**

- Prisoners or subjects who are involuntarily incarcerated.
- Subjects who are compulsorily detained for treatment of either a psychiatric or physical (eg, infectious disease) illness.
- Patients with abnormal troponins or any evidence of a recent MI

Eligibility criteria for this study have been carefully considered to ensure the safety of the study subjects and to ensure that the results of the study can be used. It is imperative that subjects fully meet all eligibility criteria.

### ***Women of Childbearing Potential***

Women of childbearing potential (WOCBP) is defined as any female who has experienced menarche and who has not undergone surgical sterilization (hysterectomy or bilateral oophorectomy) and is not postmenopausal. Menopause is defined as 12 months of amenorrhea in a woman over age 45 years in the absence of other biological or physiological causes. In addition, females under the age of 55 years must have a serum follicle stimulating hormone, (FSH) level > 40mIU/mL to confirm menopause.

\*Females treated with hormone replacement therapy, (HRT) are likely to have artificially suppressed FSH levels and may require a washout period in order to obtain a physiologic FSH level. The duration of the washout period is a function of the type of HRT used. The duration of the washout period below are suggested guidelines and the investigators should use their judgment in checking serum FSH levels. If the serum FSH level is >40 mIU/ml at any time during the washout period, the woman can be considered postmenopausal:

- 1 week minimum for vaginal hormonal products (rings, creams, gels)
- 4 week minimum for transdermal products
- 8 week minimum for oral products

Other parenteral products may require washout periods as long as 6 months.

### ***Discontinuation of Subjects from Treatment***

Subjects MUST discontinue investigational product (and non-investigational product at the discretion of the investigator) for any of the following reasons:

- Withdrawal of informed consent (subject's decision to withdraw for any reason).
- Any clinical adverse event, laboratory abnormality, or inter-current illness which, in the opinion of the investigator, indicates that continued participation in the study is not in the best interest of the subject.
- Pregnancy
  - Instruct WOCBP to contact the investigator or study staff immediately if they suspect they might be pregnant (eg, missed or late menstrual period) at any time during study participation. Institutional policy and local regulations should determine the frequency of on-study pregnancy tests for WOCBP enrolled in the study.
  - The investigator must immediately notify BMS if a study subject becomes pregnant.
- Loss of ability to freely provide consent through imprisonment or involuntary incarceration for treatment of either a psychiatric or physical (eg, infectious disease) illness.

All subjects who discontinue should comply with protocol-specified follow-up procedures outlined above. The only exception to this requirement is when a subject withdraws consent for all study procedures or loses the ability to consent freely (ie, is imprisoned or involuntarily incarcerated for the treatment of either a psychiatric or physical illness). If a subject withdraws before completing the study, the reason for withdrawal must be documented appropriately.

### **TREATMENTS**

#### **Study Treatment: DOAC or Warfarin**

**Definition of Investigational Product:** A pharmaceutical form of an active substance or placebo being tested or used as a reference in a clinical study, including products already with a marketing authorization but used or assembled (formulated or packaged) in a way different from

the authorized form, or used for an unauthorized indication, or when used to gain further information about the authorized form. In this protocol, the investigational product is DOAC.

**Definition of Non-Investigational Product:** Other medications used in the study as support or escape medication for preventative, diagnostic, or therapeutic reasons as components of a given standard of care. In this protocol, the non-investigational products are none.

### **Method of Assigning Subjects to a Treatment**

All subjects who have signed the study ICF and meet all inclusion and no exclusion criteria will be randomized in a 1:1 into one of the two study arms (1) Aspirin 81 mg or 100 mg or (2) DOAC recommended dose. For study purposes, subjects are considered enrolled in the study once they have signed the consent form and are randomized and stratified by individual sites.

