## **INVESTIGATIONAL PLAN**

### **Study Design and Duration**

This is a multicenter, randomized, prospective study to determine, if DOAC can be used periprocedural in patients undergoing a scar left ventricular arrhythmia ablation. Patients will be screened from both the clinic setting and upcoming EP lab schedule. The patient's chart will be reviewed and those that meet inclusion/exclusion will be approached for the study. For this study, we intend to enroll 52 consecutive subjects who are undergoing a scar left ventricular arrhythmia ablation at participating institutions if they meet all other inclusion criteria and do not have any exclusion criteria. Patients will be randomized in a 1:1 fashion.

Figure 1 shows the use of ASA or DOAC for left ventricular arrhythmia ablation.

[figure not shown]
Patients undergoing left ventricular arrhythmia ablation will be consented and randomized to either ASA 81 mg or 100 mg daily or DOAC twice daily. Patients randomized to ASA will continue or start ASA 81 mg or 100 mg by mouth daily, and continue up to 30 days after the procedure. Patients randomized to DOAC group will stop the ASA if they are currently taking it; DOAC 5 twice daily will be started 3 hours after hemostasis and continue for 30 days post procedure.

The drugs to which they are assigned to will be continued at least for 30 days post left ventricular arrhythmia ablation. All subjects will be followed from baseline to 30 days post procedure. At this time they will have completed the study and can stop either DOAC and/or Aspirin at the physician's discretion.

*Final revised protocol*

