### **STATISTICAL CONSIDERATIONS**

#### ***Study Management and Sample Size Justification***

This is a pilot study and 52 total patients will be enrolled in the study. We expect to analyze a total of 50 patients and each arm will consist of 25 patients. The additional 2 allows for attrition. Since this is a pilot study, the number needed to treat to achieve a pre-specified statistical significance cannot be calculated accurately. Exact sample size could not be given due to lack of pre-existing data on this subject. We hypothesize a 30% difference in outcomes can be seen with a total sample size of 50 patients.

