#### **Data Collection Center**

The Kansas City Heart Rhythm Research Foundation will be the coordinating site for the study. A project manager (PM) with the help of the PI will create the study worksheets and create the CRFs. The sites will complete the paper CRF and submit via secure email to the project manager. The PM will assist the Database Manager (DM) with updating the access database and providing computer support for outside centers. All data will be submitted via secure email including de-identified patient data that is to be used as source.

Participant's data will be de-identified and a code will be assigned. The code will consist of Site Number, Patient Number and Patient Initials. The coordinator at that site will have access to the code; the linking list will be destroyed at the completion of the project.

**Statistical analysis:** Patients will be randomized in a stratified manner to control arm versus treatment arm. We will analyze the differences in secondary endpoints between the two groups for major, minor bleeding and cardiovascular mortality up to 30 days post ablation. Categorical variables will be reported as counts and percentages and continuous variables will be expressed as mean  $\pm$  SD. Continuous variables will be compared using t-test for normally distributed data or Mann Whitney U test for non-normally distributed data as deemed appropriate. Categorical events will be compared using chi-square test for parametric data.

Univariate and multi-variate analysis will be performed to identify the predictors of systemic thromboembolic events and mortality. This is a pilot study to study the feasibility and safety of the study. A larger study will be done in the future if there is a positive signal.

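### Randomisation is stratified by site but the named between-arm tests ignore site, which makes them mildly conservative if arms are balanced within sites that differ in event rate

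*Combined protocol and SAP*

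**What the plan says.** The Study Design and Duration section describes the trial in these words: "This is a multicenter, randomized, prospective study". It adds that "Patients will be randomized in a 1:1 fashion". Under Method of Assigning Subjects to a Treatment, subjects "are randomized and stratified by individual sites". The statistical analysis paragraph, under Data Collection Center, repeats this without naming the factor: "Patients will be randomized in a stratified manner to control arm versus treatment arm".

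The same paragraph names the tests. For binary outcomes: "Categorical events will be compared using chi-square test for parametric data". For continuous outcomes: "Continuous variables will be compared using t-test for normally distributed data or Mann Whitney U test for non-normally distributed data as deemed appropriate". Site is not mentioned in the analysis text. A further analysis is planned with no covariate list: "Univariate and multi-variate analysis will be performed to identify the predictors of systemic thromboembolic events and mortality".

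On size, Study Management and Sample Size Justification says: "We expect to analyze a total of 50 patients and each arm will consist of 25 patients". The documents give no number of sites, block size or other method of forcing balance, alpha, power, or expected event rate for this population.

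**The concern.** Stratifying with balance removes differences between sites from the comparison of arms. An unstratified test still counts that between-site variation as noise, so its standard error overstates the real uncertainty. Precision gained through the design is then lost in the analysis. With 25 patients per arm, and a larger study planned if a positive signal appears, that precision has some value.

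The documents make some site differences plausible. Each institution follows its own approved ablation protocol, with operator choice of access route and epicardial approach (Ablation Protocol). Intraprocedural heparin is left to the operator's judgement (Oral Anti-Coagulation/Anti-Platelet Regimen).

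**Working it through.** **The plan's own figures.** 50 analysed + 2 for attrition = 52 enrolled, which is consistent. No stated figure bears on site, so site numbers, sizes and rates below are assumptions.

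**Formula.** With n per arm and equal allocation within equal-sized sites with rates p_s, let p̄ be their mean and w the mean of p_s(1 − p_s).
- Unadjusted standard error (SE) of the risk difference: √[2p̄(1 − p̄)/n].
- True standard deviation (SD) under within-site balance: √[2w/n].
- Ratio: √[p̄(1 − p̄)/w]. Since p̄(1 − p̄) = w + the variance of p_s between sites, the ratio exceeds 1 only when sites differ.

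**Numbers put in** (four sites of 12, n = 24 per arm):
- Rates 5/15/35/55%: p̄ = 0.275, p̄(1 − p̄) = 0.1994, w = 0.65/4 = 0.1625. Ratio √(0.1994/0.1625) = 1.108.
- Rates 2/8/16/30%: p̄ = 0.14, p̄(1 − p̄) = 0.1204, w = 0.4376/4 = 0.1094. Ratio √(0.1204/0.1094) = 1.049. The mean of 14% matches the only MRI lesion rate in the documents, which comes from atrial fibrillation ablation (Overall Risk/Benefit Assessment).

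The formula is a large-sample one. With 48 patients the estimated SE runs a little low, so the simulated excess is smaller.

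**Simulation, balanced within site** (200,000 runs, two-sided 5%, chi-square without continuity correction; power is for a 70% relative reduction in every site):

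| Site rates | Mean SE / true SD | Type I error: chi-square, CMH | Power: chi-square, CMH |
|---|---|---|---|
| 5/15/35/55% | 0.1275/0.1161 = 1.098 | 3.2%, 5.0% | 43.4%, 45.8% |
| 2/8/16/30% | 0.0981/0.0954 = 1.028 | 4.3%, 4.6% | 19.5%, 19.6% |
| all 14% | 0.0978/0.1003 = 0.975 | 5.3%, 5.3% | 20.2%, 20.2% |
| all 27.5% | 0.1272/0.1287 = 0.988 | 5.2%, 4.9% | 43.7%, 43.1% |

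**Without forced balance** (simple randomisation within site), mean SE / true SD is 0.989 for rates of 5 to 55% and 0.976 for 2 to 30%. The SE is not too wide. Chi-square type I error is 5.1% and 4.9%. In five sites of 10 it is about 5.7% both when all rates are 50% and when they run from 10 to 90%. That small excess is a small-sample feature of the uncorrected chi-square, not an effect of site.

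**A different layout** (five sites of 10, permuted blocks of 4, 15,000 runs). Type I error, chi-square against CMH:
- rates 5 to 25%: 4.6% against 4.7%
- rates 10 to 50%: 4.0% against 4.7%
- rates 10 to 90%: 3.0% against 5.1%

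Power for a 30-point drop, chi-square against CMH:
- control rates 30 to 70% across sites: 63.4% against 65.0%
- all sites at 50%: 63.4% against 60.4%
- all sites at 50%, simple randomisation: 61.9% against 57.0%

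**An exact alternative.** Re-randomising treatment labels within site (four sites of 12, 40,000 runs) gives type I error of 2.1% and power of 31.6% for rates of 5 to 55%. For 2 to 30% it gives 1.7% and 8.1%. With so few events the test is very discrete, and it is more conservative than the planned chi-square.

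**The case against.** The strongest objection is that the premise is not in the documents. Stratified lists balance the arms within site only if blocking or a similar device is used, and none is stated. Without it the excess disappears. This stands, so the conclusion is conditional. Balance is the usual purpose of stratifying, but the protocol should say how it is achieved.

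The second objection is size. The larger figure needs an 11-fold spread in site rates (5% to 55%). With rates averaging 14%, the type I error differs by 0.3 points and power by 0.1. In a pilot of feasibility and safety with no power target, that is little. This also stands, and it sets the priority.

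Third, a site-stratified test can lose power when sites do not differ. This stands as a cost of the change.

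Two stronger readings are tempting, and the text does not support them:
- A reader might infer that every planned analysis ignores site. The multivariable analysis lists no covariates, so site is neither included nor excluded. The accurate statement is limited to the named between-arm tests.
- A reader might infer from the reference to institutional protocols under Cerebral MRI that lesion detection differs by site. That reference concerns patients with implanted devices, for whom Attachment A supplies a common algorithm. The section itself fixes field strength, sequences and lesion definition, and calls for blinded reading.

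Event rates also have no bearing on the continuous comparisons. There the parallel argument concerns site differences in means.

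**Conclusion.** The mismatch is real: site is used to randomise and is absent from the named between-arm tests. The consequence is conditional and mild. If arms are balanced within site and event rates differ, the simulated standard error is about 2 to 3% too wide for site rates of 2 to 30% and about 9 to 10% too wide for 5 to 55%. The large-sample formula gives 4.9% and 10.8%. If rates are equal, or balance is not forced, there is no excess.

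A reader might take this as a threat to validity. It is not: the error is in the conservative direction, type I error is not inflated by ignoring site, and no bias follows. The sizes rest on assumed sites of equal size and assumed rates. Low priority.

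**What to change.** Under Method of Assigning Subjects to a Treatment, state how allocation is done within site, for example permuted blocks.

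In the statistical analysis paragraph:
- For binary endpoints, make the arm comparison a Mantel-Haenszel risk difference stratified by site, with its confidence interval, and a CMH test by site.
- For continuous outcomes, include site as a factor.
- Pool very small sites by a rule fixed before data lock.
- Do not substitute an exact within-site re-randomisation test, for the reason shown in the calculation.

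This costs a few sentences and a little programming. The patient code already contains the site number. The statistical cost is a power loss when sites do not differ: 0 to about 3 points in the balanced simulations, and about 5 points in the one with unblocked allocation (61.9% − 57.0%). Very small or one-arm sites will add little to the stratified estimate. If the sponsor prefers the unstratified tests, a stated reason would be enough.

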### **Selection and Timing of Dose for Each Subject**

DOAC should not be used if a patient has an allergy or has had active pathological bleeding where the use of the agent is contraindicated. Similarly, patients who are allergic and contraindicated to ASA should not use ASA.

If a dose of DOAC is not taken at the scheduled time, the dose should be taken as soon as possible on the same day and then continue with twice daily administration as before. The dose should not be doubled to make up for a missed dose. DOAC can be taken with or without food.

DOAC is not recommended in patients with severe hepatic impairment. These patients will not meet the inclusion/exclusion criteria.

### ***Dose Modifications***

Dose modification per investigator recommendations and per current guidelines.

### **Concomitant Treatments**

#### ***Prohibited and/or Restricted Treatments***

Co-administration of the maintenance dose of DOAC is not recommended with drugs that increase the risk of bleeding (eg, other anticoagulants, heparin, thrombolytic agents, NSAIDs, SSRIs, serotonin norepinephrine reuptake inhibitors).

### ***Other Restrictions and Precautions***

DOAC should be discontinued 48 hours prior to elective surgery or invasive procedures. If surgery or invasive procedures cannot be delayed, exercise appropriate caution taking into consideration an increased risk of bleeding. This risk of bleeding should be weighed against the urgency of intervention.

Use DOAC with caution when co-administered with nonsteroidal anti-inflammatory drugs (NSAIDs), including ASA.

